6.3.11 Other Safety Assessments

Clinical Laboratory Measurements

For the laboratory parameters presented below and assessed at the 5-7-years follow-up visit, summary statistics will be produced for observed values at pre-transplantation, transplantation, week 1, week 7-11, month 3, month 6, month 12, 3-years follow-up and 5-7-years follow-up visit. In addition, the difference from baseline to each visit at which they were assessed will be derived and presented by treatment group and in total.

Abnormal (low and high) values will be flagged in listings.

Shift tables that show the number of patients who changed from low, normal or high at baseline to low, normal or high at each post-baseline time of assessment will be presented.

In case laboratory values are below the limit of quantification, the value corresponding to the limit of quantification will be used when summarising data (e.g. if the result is <x.x then the value x.x will be used in the statistical analysis).

Clinical chemistry/Biochemistry	Lipid profile	Hematology	Urinalysis
Serum creatinine	Total Cholesterol	Hemoglobin	Albumin/Creatinine ratio
S-Sodium	LDL- Cholesterol	Leucocytes	
Potassium	HDL- Cholesterol	Platelet count	
Alanine	Triglycerides (TG)		
Aminotransferase (ALAT)			
Aspartate			
Aminotransferase (ASAT)			
Urea			
Uric Acid			
Albumin			
HbA1c			
NT-proBNP			
Troponin-T			
C-reactive protein (CRP)			

Vital Signs

The vital signs parameters (height, weight, Body Mass Index (BMI), heart rate, systolic and diastolic blood pressure) will be presented at pre-transplantation, transplantation, week 1, week 4, week 7-11, month 3, month 6, month 9, month 12, 3-years follow-up and 5-7-years follow-up visit by summary statistics for observed values and change from pre-transplantation by treatment group and in total.

Electrocardiogram

The Electrocardiogram (ECG) parameters (heart rate, PQ-time and QRS) will be presented at transplantation, week 7-11, month 12, 3-years follow-up and 5-7-years follow-up visit by summary statistics for observed values by treatment group and in total.

Type of rhythm will be presented by a shift table showing the number of patients who changed from Sinus rhythm, Other or NA/ND/UNK at baseline to Sinus rhythm, Other or NA/ND/UNK at each post-baseline time of assessment by treatment group.

Cardiac Rejections

The number of patients with at least one cardiac rejection (grade I-III): cellular, humoral or mixed, will be presented by treatment group for three periods: during the main study, between main study to 3-years follow-up and between 3-years follow-up to 5-7-years follow-up.

Also the total number of cardiac rejection (grade I-III): cellular, humoral or mixed, and the total number of treated cardiac rejection will be presented by treatment group for the three periods.

Information regarding mixed cardiac rejection was only collected for during the main study and 3-years follow-up. During main study and at the 3-years follow-up visit, date of when a biopsy performed was collected. A biopsy confirmed rejection within 13 days from previous biopsy confirmed rejection was considered the same event. Thus, the same rejection could go on for several weeks.

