4.3.7 Cardiac rejections

Number and grading of biopsy proven and treated rejections and rejections with hemodynamic compromise since the 3 year follow-up visit will be collected.

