6.3.3 Patient Data Listings

Data collected in the Case Report Form (CRF) will generally be listed in Appendix 16.2. CRF check questions [e.g. lab samples taken (Yes/No)] and reminders will not be listed.

Listings will be sorted by treatment group, enrollment number and randomization number.

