14.3 SAFETY DATA

(Safety presentations will be based on the Safety set if not other is stated below)

- 14.3.1.x Summary of Adverse Events
- 14.3.1.x Adverse Events by System Organ Class and Preferred term
- 14.3.1.x Summary of Serious Adverse Events
- 14.3.1.x Serious Adverse Events by System Organ Class and Preferred term
- 14.3.2 Listings of Deaths, Other Serious and Significant Adverse Events
- (14.3.3 *this title is reserved for narratives*)
- 14.3.4.x Abnormal Laboratory Value Listing (low and high, if reference values available)
- 14.3.4.x Other Relevant Laboratory Analyses:
 - Clinical chemistry/Biochemistry (summary statistics for observed values and change from baseline by treatment group and total values)
 - Lipid profile (summary statistics for observed values and change from baseline by treatment group and total values)
 - Hematology (summary statistics for observed values and change from baseline by treatment group and total values)
 - Urinalysis (summary statistics for observed values and change from baseline by treatment group and total values)
 - Shift Tables Clinical chemistry/Biochemistry
 - Shift Tables Lipid profile
 - Shift Tables Hematology
 - Shift Tables Urinalysis
- 14.3.5.x Extent of Exposure (Safety set, ITT, PPS, extended PPS)
 - Ongoing Immunosuppressive Treatments at 5-7-years Follow-Up (frequency table)
 - Dose Rate of Immunosuppressive Treatments from the End of the Main Study to the 5-7-years Follow-Up Visit (summary statistics)
 - Trough Blood Levels at 5-7-years Follow-Up (summary statistics for observed values)
- 14.3.6 Vital signs (summary statistics for observed values and change from pre-transplantation by treatment group and in total)
- 14.3.7.x ECG (summary statistics for observed values)
 - Shift ECG for Type of Rhythm

14.3.8.x Cardiac Rejections (frequency table by treatment group)

- Number of patients with at least one cardiac rejection (grade I-III): cellular, humoral or mixed (for three periods: during the main study, between main study to 3-years follow-up and between 3-years follow-up to 5-7-years follow-up)
- Total number of cardiac rejection grade I-III (cellular, humoral or mixed, for three periods: during the main study, between main study to 3-years follow-up and between 3-years follow-up to 5-7-years follow-up)

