- Total number of treated cardiac rejection grade I-III (for three periods: during the main study, between main study to 3-years follow-up and between 3-years follow-up to 5-7-years follow-up)

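### In the public SAP text, treated rejections appear only as an event total per arm and period, so the number of patients with a treated rejection is generally not identified.

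*SAP*

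**What the plan says.** SAP 6.3.11, under Cardiac Rejections, plans three summaries for each arm and each of three periods (main study, main study to 3-year visit, 3-year visit to 5-7-year visit):

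- a patient count: "The number of patients with at least one cardiac rejection (grade I-III): cellular, humoral or mixed, will be presented by treatment group";
- an event total: "Also the total number of cardiac rejection (grade I-III): cellular, humoral or mixed";
- a treated-event total: "the total number of treated cardiac rejection will be presented by treatment group for the three periods".

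Table 14.3.8.x in SAP Appendix 1 repeats the same three items. Its two event rows are titled "Total number of cardiac rejection grade I-III" and "Total number of treated cardiac rejection grade I-III". No redaction mark appears among the three items.

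The protocol collects more than this table uses. Protocol 4.3.7 states: "Number and grading of biopsy proven and treated rejections and rejections with hemodynamic compromise since the 3 year follow-up visit will be collected". SAP section 5 assigns safety presentations to the Safety Set. Individual rejections go into listing 16.2.11.

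**The concern.** Protocol 1.1 credits calcineurin inhibitors with low acute rejection rates, and Group B had its calcineurin inhibitor withdrawn. Rejection is therefore the foreseeable harm to set against a renal benefit. A reader will want to know what share of patients in each arm had a rejection that needed treatment or that compromised the circulation.

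The planned rows do not answer this directly. An event total lets one patient with several treated rejections look like several patients. The only patient count covers any rejection of grade I-III, so it includes rejections that were never treated. Hemodynamic compromise, arguably the most clinically telling feature collected, has no row in the visible text.

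**Working it through.** **Inputs.** The three rows come from SAP 6.3.11 and table 14.3.8.x. The documents state no rejection rate, so there is no planned figure to reproduce, and the question is what the rows can determine. For one arm and period, let P = patients with at least one rejection, E = all rejections, T = treated rejections, and k = patients with at least one treated rejection. P, E and T are planned; k is not.

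**Bounds on k, for T > 0.**

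1. Each treated patient has at least one treated rejection and is among the P patients, so 1 ≤ k ≤ min(T, P).
2. Each of the other P − k patients has at least one untreated rejection. Hence E − T ≥ P − k, which gives k ≥ P + T − E.
3. Together: max(1, P + T − E) ≤ k ≤ min(T, P).
4. Every whole number in this range is attainable. Give each of the k patients one treated rejection and put the remaining T − k treated rejections among them. Give each of the other P − k patients one untreated rejection, and place the leftover untreated rejections anywhere. Enumeration of all 490 combinations with P = 1 to 7, E = P to 12 and T = 1 to E gives the same range every time.

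**When k is known exactly.** The width of the range is min(min(T, P) − 1, E − max(T, P)). It is zero only if E = P (no repeat rejections), E = T (all treated), T = 1 or P = 1. The case E = T would arise in the latest period if only treated rejections were recorded, which is one possible reading of Protocol 4.3.7. The SAP's separate rows for all and for treated rejections in every period suggest otherwise.

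**Illustration, all figures assumed.** Take 51 patients per arm, which is 102 / 2. The 102 attended the 3-year visit (SAP 4.1); the split by arm is not given, and the Safety Set may be smaller. Let P = 20 in both arms, T = 8 in one and 4 in the other, with the same E in both.

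| E | k when T = 8 | k when T = 4 |
|---|---|---|
| 20 | 8 (15.7%) | 4 (7.8%) |
| 23 | 5 to 8 (9.8% to 15.7%) | 1 to 4 (2.0% to 7.8%) |
| 24 | 4 to 8 (7.8% to 15.7%) | 1 to 4 |
| 25 | 3 to 8 (5.9% to 15.7%) | 1 to 4 |

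For example, at E = 25 and T = 8 the lower limit is 20 + 8 − 25 = 3. For T = 4 it is max(1, 20 + 4 − 25) = 1. Up to E = 23 the order of the arms cannot change. At E = 24 a tie is possible, and from E = 25 a reversal is arithmetically possible.

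**Hemodynamic compromise.** Setting Protocol 4.3.7 beside SAP 6.3.11 and table 14.3.8.x, the item is collected for the period since the 3-year visit and no visible row uses it.

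**The case against.** **Other outputs cover this in part.** Rejection is a selected adverse event in Protocol Table 2, and SAP 6.3.10 counts each preferred term once per patient, so the SAE tables give patients per arm with a serious rejection. Table 14.3.2 lists deaths and other serious events. For listing 16.2.11, SAP 6.3.3 says "Listings will be sorted by treatment group, enrollment number and randomization number", so a reader could count treated patients by hand if treated status is shown. This stands as partial cover. No AE table is specified by treated status, and a listing is not a per-arm summary.

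**A reader might infer that the count is tabulated nowhere.** The documents do not support so flat a claim. SAP numbering jumps from 6.3.6 to 6.3.8 and from 6.6 to 6.8, and section 5 has a redacted class of variables. Nothing visible points to a rejection table there, but the claim is limited to the public text.

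**A reader might infer that patients with higher-grade rejection cannot be counted.** Pooling is the plain reading of grade I-III, but Appendix 1 lists table titles rather than shells, so rows by grade are not strictly excluded. Protocol Table 2 attaches a grade to cellular rejection only, and no common scale across cellular, humoral and mixed rejection is defined.

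**A reader might infer that the table would mislead on which arm is worse.** The reversal at E = 25 is a corner case. Three patients must hold all eight treated rejections and no untreated one, the other 17 must have exactly one untreated rejection each, and the four treated rejections in the other arm must fall in four different patients. For the main study and 3-year data, the SAP also describes merging biopsy-confirmed rejections within 13 days of each other, which moves E towards P and narrows the range.

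**Earlier periods may already be reported.** The 12-month report and the 3-year addendum are not among the documents and may hold these counts. This stands, so the gap is clearest for the period since the 3-year visit.

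**Rejection is neither a primary nor a named secondary endpoint, and no test depends on it.** This stands, and it is why the point is minor.

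**Conclusion.** The point holds as a minor gap in descriptive safety reporting. In the public SAP text, treated rejections are summarised only as events, and the one patient count is for any rejection of grade I-III. When patients have repeat rejections, the number with a treated rejection is generally identified only to within max(1, P + T − E) and min(T, P). It is exact in the special cases given above. How wide the range will be cannot be said from the documents, because they give no rejection rates. The illustration shows scale and predicts nothing. The absence of a visible row for hemodynamic compromise follows from the text and needs no assumption.

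The conclusion rests on the visible text being complete for table 14.3.8.x and on treated rejections being a subset of those counted. It says nothing about which arm has more rejection, and the primary mGFR comparison is unchanged.

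**What to change.** Keep the three existing rows in SAP 6.3.11 and table 14.3.8.x. For the period since the 3-year visit, add by arm the number (%) of Safety Set patients with:

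- at least one treated rejection;
- at least one rejection with hemodynamic compromise.

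Add the treated-patient row for the two earlier periods only where the data allow. If grade is reported, give the highest grade separately by rejection type (for example cellular), not one highest grade across all types. No tests are needed.

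The cost is a few words in the SAP and two rows in one table. Protocol 4.3.7 already provides for the data in the latest period, so nothing new has to be collected. Cell counts will probably be small and should be read as description only.

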6.4 Level of Significance, Multiple Comparisons and Multiplicity

The primary comparison will be performed on one single variable at one single occasion no adjustment of the statistical significance level will be made for multiple analyses. [REDACTED]

[figure not shown]
6.5 Adjustment for Covariates

Baseline measurement for mGFR will be used as covariate and stratum as classification variable in the ANCOVA.

6.6 Handling of Dropouts and Missing Data

Outliers will be included in summary tables, and will not be handled separately.

[REDACTED]

[figure not shown]

Exposure of immunosuppressive treatments: If start date and/or end date is incomplete after Data Management processing, the following will be assigned for the missing **start** date:

- if no field is available: Month 12 (Visit 11) date of main study will be imputed
- if only the year is available: Day “01” and month of “July” will be imputed
- if the month and year are available: Day “15” will be imputed
- if start date is before transplantation date (Visit 2) will be imputed

The following will be assigned for the missing **end** date:

- if no field is available, i.e. the treatment is ongoing: 5-7-years follow-up date will be imputed
- if only the year is available: Day “01” and month of “July” will be imputed
- if the month and year are available: Day “15” will be imputed

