6.3.8 Exposure to Treatment

The ongoing immunosuppressive treatments:

- Everolimus
- Cyclosporine (Control)
- Tacrolimus (Control)
- Prednisolone
- Mycophenolate mofetile (MMF)

will be presented by a frequency table.

The dose rate, daily dose registered in the Immunosuppressive Medication CRF-page at 5-7-years follow-up visit/time registered in the Immunosuppressive Medication CRF-page at 5-7-years follow-up visit, that was consumed by each patient will be presented in a summary table from end of main study until the 5-7-years follow-up visit. If start date is missing, end date of main study will be used (see Section 6.6).

The observed trough blood levels for Cyclosporine, Everolimus and Tacrolimus for the 5-7-years follow-up visit will be presented in a summary table.

The safety set, ITT, PPS and extended PPS population will be used and presented by treatment group and in total.

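### The partial-date rule for immunosuppressive drugs does not check stop against start or cap dates at the visit, so some dose rates would be undefined or negative

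*SAP*

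**What the plan says.** The rule is in SAP 6.6 and applies to drug exposure only: "Exposure of immunosuppressive treatments: If start date and/or end date is incomplete after Data Management processing". It has one list for start dates and one for end dates. Two lines are the same in both:

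- Year known: "if only the year is available: Day “01” and month of “July” will be imputed".
- Month and year known: "if the month and year are available: Day “15” will be imputed".

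A start with nothing recorded goes to the end of the main study: "if no field is available: Month 12 (Visit 11) date of main study will be imputed". An end with nothing recorded is treated as ongoing: "if no field is available, i.e. the treatment is ongoing: 5-7-years follow-up date will be imputed". The start list has one further line, with words apparently missing: "if start date is before transplantation date (Visit 2) will be imputed". I read it as moving a start before transplantation up to the transplantation date.

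SAP 6.3.8 uses these dates. It defines a dose rate as the registered daily dose divided by the registered time. The result "will be presented in a summary table from end of main study until the 5-7-years follow-up visit", for the safety set, ITT, PPS and extended PPS. SAP 6.6 also keeps outliers in the summary tables without separate handling.

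**The concern.** A midpoint rule works when the other end of the course and the visit are far away. It fails when they fall in the same year or month as the partial date. The fixed date can then land on the wrong side of a date already known, and the SAP has no line that prevents this.

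Such courses are plausible. Protocol 4.3.2 collects starts and stops since the end of the main study, and Protocol 4.2 and SAP 4.1 both say that patients may have changed drugs. A drug tried for a few months, or one started in the year of the visit, is enough to trigger the problem.

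At stake is the dose-rate table. Time is the denominator, so zero time gives no value, negative time gives a negative rate, and very short time gives a very large one. SAP 6.3.2 reports mean, standard deviation, minimum and maximum. At most 102 patients attended the 3-year visit, so a single such value can distort a row.

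**Working it through.** The plan gives no figure to reproduce, so the check applies the rule as written.

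**Inputs from SAP 6.6.** Year only becomes 1 July. Month and year become the 15th. A missing start becomes the Month 12 date. A missing end becomes the visit date. A start is no earlier than transplantation (as I read the incomplete line). The calendar dates below are my assumptions, since the documents give no patient dates.

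**Formula.** Length = stop - start, in days.

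| Recorded | Start used | Stop used | Length |
|---|---|---|---|
| Start 15 Oct 2014, stop 2014 | 15 Oct 2014 | 1 Jul 2014 | -106 |
| Start 2014, stop 20 Mar 2014 | 1 Jul 2014 | 20 Mar 2014 | -103 |
| Start 20 May 2014, stop May 2014 | 20 May 2014 | 15 May 2014 | -5 |
| Start missing (Month 12 on 20 Oct 2011), stop 2011 | 20 Oct 2011 | 1 Jul 2011 | -111 |
| Start 2016, ongoing, visit 15 Mar 2016 | 1 Jul 2016 | 15 Mar 2016 | -108 |
| Start 2014, stop 2014 | 1 Jul 2014 | 1 Jul 2014 | 0 |
| Start May 2014, stop May 2014 | 15 May 2014 | 15 May 2014 | 0 |

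For the first row, 1 July to 15 October is 31 + 31 + 30 + 14 = 106 days. For the fifth, 15 March to 1 July is 17 + 30 + 31 + 30 = 108 days.

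**Does the existing limit help?** No. Every start in the table is at or after Month 12, so a floor at transplantation changes nothing.

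**Effect on the dose rate.** With daily dose D, the first row gives D / (-106), which is negative. The last two rows give D / 0, which is undefined. Counting inclusively (stop - start + 1) turns 0 into 1 but only moves -106 to -105.

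**How often?** The documents do not allow an estimate. A conditional figure can be given if dates are uniform over one calendar year and start and stop fall in the same year:

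- Full start, year-only stop: the length is negative when both true dates fall after 1 July, (184/365)² = 0.254. A simulation of 1,000,000 pairs also gave 0.254.
- Year-only start, full stop: (181/365)² = 0.246.
- Year-only start in the visit year, ongoing: a uniformly distributed visit date falls before 1 July with probability 181/365 = 0.496, and the imputed start is then after the visit.

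These are proportions of courses of exactly that kind, not of all courses.

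**The case against.** The strongest reply is that this hardly matters. The primary ANCOVA in SAP 6.3.5 uses no treatment dates. PPS and extended PPS membership in SAP 5 rests on the treatment recorded at the visit. Of the exposure tables in SAP Appendix 1 (14.3.5.x), only dose rate uses the dates; the others show ongoing treatments and trough levels. The rule applies only to what remains after data management, Protocol section 5 requires CRF entries to be traceable to source documents, and listing 16.2.5 would show an impossible course. All of this stands, and it limits the point to a minor one.

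It does not remove the error. Data management may reduce the number of partial dates but sets no limits on imputed ones. The period named in SAP 6.3.8 is a reporting window and does not say what to do with a start that falls after it. The listing may reveal a negative course, but the SAP gives no rule for correcting it and keeps outliers in. Any repair would be improvised, possibly after database lock in an open-label study.

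A reader might also infer that a drug taken up by switching, with no start date, should start when the replaced drug stopped. The Month 12 fallback can overstate such a course. However, the documents do not show that the CRF links a started drug to the one it replaced. Overlap is not in itself an error either, since the extended PPS allows everolimus together with CsA or tacrolimus.

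**Conclusion.** The point holds as a minor one. Read literally, SAP 6.6 produces courses of zero or negative length and starts after the visit, and SAP 6.3.8 then gives undefined or negative dose rates. The damage is limited to one descriptive table shown for four analysis sets. Its size in this trial is unknown, because the number of partial dates is not stated. The conclusion assumes the rule is programmed as written. Redacted text in SAP 6.6 stands before the exposure paragraph, and the exposure rule itself shows no redaction.

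Four stronger readings are tempting and not supported:

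- That the rule has no bounds at all. It has a lower limit for starts, although that limit prevents none of the failures shown.
- That a quarter of courses would be negative. The 25% is hypothetical and applies only to same-year courses with a full start, a year-only stop and uniform dates.
- That the partial dates belong mainly to switched patients or come from recall. The documents say neither.
- That exposure-duration tables or the treatment comparison are affected. No duration table is planned, and the primary comparison does not use the dates.

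**What to change.** Replace the fixed-date lines in SAP 6.6 with a rule that imputes within a feasible window, inside the known year or month:

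- A start lies between transplantation and the earlier of the stop and the visit.
- A stop lies between the start (including one imputed to Month 12) and the visit.
- Keep 1 July or day 15 when it falls inside the window; otherwise use the window's midpoint.
- When both dates are partial in the same period, impute them jointly so that start precedes stop, for example at one third and two thirds of the window.
- Count time as stop - start + 1.
- Complete the wording of the transplantation-date line.

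Applied to the two main examples (the first assumes a visit after 2014):

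- Stop in 2014 after a start on 15 October: the window runs to 31 December, 77 days. The midpoint is 22 November 2014, and the length is 38 + 1 = 39 days.
- Start in 2016 before a visit on 15 March: the window from 1 January is 74 days. The midpoint is 7 February 2016, and the length is 37 + 1 = 38 days.

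Moving a date only as far as the known start or the visit is not enough. Both examples would then have 0 days, or 1 day counted inclusively, which inflates the dose rate.

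The cost is a few lines of SAP text and minor programming before database lock. No new data are needed.
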